1 PROTOCOL SYNOPSIS

Protocol Title:	Feasibility Study for VCool Intranasal Cooling System in Healthy Volunteers
Protocol Number:	00080424
Version:	2.0
Date:	01 August 2024
Development Phase:	Pilot Study
Sponsor:	NeuroIntact, Inc. [name]
Study Objective:	The objective of this study is to evaluate the performance and safety of the VCool Intranasal Cooling System in healthy adult volunteers. The study is designed to gather preliminary data regarding air flow rates and time required to reduce core body temperature to 35.5°C and maintain the temperature between 35°C and 36°C for one hour after cooling.
Number of Sites / Number of Participants:	The study will be conducted at one site in Maryland. A total of 10 participants need to complete the study.
Primary Endpoints:	
1. To confirm the VCool System can lower core body temperature to 35.5°C within 2 hours.2. To confirm the VCool System can maintain a core body temperature between 35°C and 36°C for one hour after cooling.3. To demonstrate the differential impact of VCOOL system between core body and brain temperature
Secondary Endpoint:	
1. To assess the shivering experienced by participants based on the 4-point Bedside Shivering Assessment Scale (BSAS).
Safety Evaluation:	All treatment emergent adverse events (TEAEs) reported by participants will be tabulated. Each adverse event (AE) will be evaluated by the Investigator in terms of seriousness, severity (mild, moderate, severe) and relationship (not related, possibly related, probably related, definitely related) to the study device.
Study Design:	This is a single-center, prospective, open label, feasibility study in healthy adult participants. Participants will be monitored for up to 2 hours while using the VCool System to determine if the target temperature of 35.5°C is reached. If the target core body temperature is reached within 2 hours, the participant will be monitored for an additional hour to determine if the VCool System can maintain the participant's core body temperature between 35°C and 36°C for one hour.

	During the study, the participants will have their blood pressure and temperature monitored and will be assessed for shivering and adverse events.
Study Duration:	The overall study participation for each participant will be one visit lasting approximately 4 hours. Study enrollment is anticipated to be completed within two weeks.
Study Device:	VCool Intranasal Cooling System
Proposed Indication for Use:	The VCool Intranasal Cooling System is intended for temperature reduction in adult patients where cooling is indicated.
Eligibility Criteria:	
Participants who meet all the inclusion criteria and none of the exclusion criteria are eligible for enrollment in the study.
 
Inclusion Criteria
 
1. Male or female ages 18 to 55.2. An Institutional Review Board (IRB) approved informed consent is signed and dated prior to any study-related activities.3. Baseline core body temperature between 36.8°C and 37.5°C.4. Have the ability to understand the requirements of the study and are willing to comply with all study procedures.5. In the opinion of the Investigator, are able to participate in the study. 
Exclusion Criteria
 
1. History of cardiovascular, respiratory, or metabolic disorder2. Any contraindication to undergoing Magnetic Resonance Imaging (MRI)3. Pregnant4. Severe peripheral vascular disease5. History of Raynaud's disease6. Currently experiencing a respiratory infection7. Chronic rhinosinusitis8. History of sickle cell disease9. History of cold agglutinin disease10. History of cryoglobulinemia11. Known deviated septum or nasal deformity12. History of nosebleeds or a nosebleed within past 24 hours

	13. Use of antipyretics or other medications affecting body temperature within the past 24 hours.
--	---

2 INTRODUCTION

2.1 Background

Inducing normothermia or mild hypothermia is known to have therapeutic benefits in various medical conditions where neuronal damage can occur, including stroke and cardiac arrest patients [1-9]. Among numerous benefits, cooling, known as Targeted Temperature Management (TTM), has been shown to reduce cerebral edema and neurogenic fever. Numerous studies have been completed inducing normothermia or mild hypothermia in healthy volunteers using different cooling technologies including surface and intravascular approaches with no serious adverse events [10-14]. This study is the first to use thermoelectrically cooled air delivered through the nasal passages via nasal cannula to reduce core body temperature.

The VCool Intranasal Cooling System has been previously studied in a porcine animal model which demonstrated safety and efficacy [15]. In this study, swine were cooled and met the primary outcome of effective cooling (34°C from 38.1°C) There was no secondary short or medium evidence of injury in CT imaging of the animal's snout anatomy, CT perfusion of the brain, or histological analysis of the brain and snout.

2.2 Study Objective

The objective of this study is to evaluate the performance and safety of the VCool Intranasal Cooling System (VCool) in healthy adult volunteers. The study is designed to gather preliminary data regarding air flow rates and time required to reduce core body temperature to 35.5°C and maintain the temperature between 35°C and 36°C for one hour after cooling. Additional data will be obtained on whether intranasal cooling results has a differential temperature impact on core body temperature as compared to brain temperature.

The data collected will help to develop automated cooling models and the control system algorithm by examining participant cooling response as a function of air flow rate and time the air is supplied to the participants.

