3 STUDY DEVICE

3.1 Device Description

The VCool Intranasal Cooling System is intended to cool the core body temperature of patients for whom cooling is medically indicated. The VCool System produces a flow of thermoelectrically cooled air from an external source (hospital compressed wall medical air or oxygen). The air flow is delivered from the VCool System to the patient via an insulated air delivery tube. The air delivery tube is insulated to keep the air cooled. A two-prong nasal cannula is attached to the delivery tube and placed in the patient's nostrils. Cooled air enters the nasal passages and exits freely through the nose and mouth. The nasal prongs do not create a seal at the nostrils and therefore do not create excess airway pressure. The VCool System does not utilize invasive catheters, surface cooling pads, or any cooling agents. The VCool System is not used to deliver respiratory support.

The VCool is a small device weighing less than 25 pounds. There is an internal power source, a Peltier (thermoelectric cooling unit), air tubing, and thermistors. The system can deliver air flow rates of up to 40 liters per minute set to a temperature of 5°C at the end of the cannula. All parts of the system are constructed of biocompatible materials and designed for electrical safety. In this study, the VCool will be connected to a medical grade air compressor which will supply the air for cooling. A commercially available nasal cannula will be used to deliver the cooled air.

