7.6 Procedure

7.6.1 **VCool System Set Up**

Attach the disposable delivery tube to the VCool System

Install the gas inlet filter on the back with the filter bowl vertical (glass side down)

Attach the air hose to the gas inlet filter

Connect the power cord to a grounded outlet

Turn the power switch to "ON"

Connect the RS232 cable to the VCool System and to the laptop computer

Turn on the computer

Select the following:

TC-48-20 program.

COM5

Communications

Set Point and set value to -19.0

Controller options

Save data to file

Go to file Explorer, select LabView Data

Select New and enter participant identification number as file name

Save data to file

Turn on gas and set flow meter to 35 liters per minute.

Confirm temperature is set to -10°C

Confirm gas temperature setting at the end of the delivery tube is -5°C

Attach nasal cannula to the delivery tube

7.6.2 *MR Imaging procedure*

- Participants will undergo MRI at the HSF3 research facility at the University of Maryland, Baltimore (UIMB). Each imaging session will last approximately 90 minutes. The protocol will include high-resolution anatomical MRI for structural reference and tissue segmentation; MR Spectroscopy (MRS) to measure metabolite and water resonance frequencies for temperature estimation; MR Thermometry to measure phase changes over time to track temperature dynamics; Perfusion MRI to measure cerebral blood flow (CBF); as well as other structural and functional imaging sequences. These sequences will be repeated at multiple time points during the controlled cooling period to monitor temporal changes in temperature, perfusion, and tissue properties.

7.6.3 *Participant Set Up and Monitoring*

Have the participant lie on their back in an inclined position and place the nasal cannula on the participant, securing the straps around their head

Record the temperature from both temperature sensors and record the time

Record the flow rate

Initiate the cooling and record the time. The induction phase for participant cooling can take up to 2 hours.

Record the core body temperature every 2 minutes from both temperature sensors and record the time. The core body temperature is monitored throughout the study.

If the core body temperature is <35°C for 5 minutes:

1. Remove nasal cannula, if temperature starts to rise after 2 minutes keep cannula off until temperature gets back to 35°C. Then reapply nasal cannula and resume treatment.

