2. If temperature continues to fall below 35°C after 2 minutes, cover patient with electric blanket that has been pre heated on standby. Keep blanket on until temperature gets back to 35°C.

Assess for shivering every 10 minutes using the BSAS. Record the results and time. The BSAS is recorded throughout the study.

Bedside Shivering Assessment Scale

0	None
1	Mild: Shivering localized to neck/thorax
2	Moderate: Intermittent involvement of the upper extremities and/or thorax
3	Severe: Generalized shivering or sustained upper and/or lower extremity shivering

The flow can be increased to 40 liters per minute after 10 minutes

Record any VCool System adjustments to flow rate or temperature and record the new flow rate and temperature and time of adjustment. Record the reason for the adjustment.

Assess the participant for adverse events (AEs) throughout the study

If the participant has a nosebleed, discontinue the study and note the time.

Monitor patient at first sign of shivering

- If **Mild**, cover patient with regular blanket.
- If **Moderate or severe** – discontinue cooling treatment.

Continue to record the temperature until either temperature sensor reaches 35.5°C or the VCool System has been used for 2 hours. Note the time the target temperature was achieved.

If the participant's core body temperature does not reach 35.5°C in 2 hours, the study is concluded

- Remove the nasal cannula from the participant and dispose of it properly
- Monitor the participant's core body temperature until it returns to baseline. Blankets can be applied to help with warming.
- Remove the axillary thermometer

If the participant's core body temperature reaches 35.5°C, proceed to the next steps

Maintain the target temperature of 35.0°C to 36.0°C for 1 hour:

Adjust flow rate by 5 liters per minute from baseline every 2 minutes

- If temperature falls below 35°C., reduce flow rate by 5 liters per minute every 2 minutes until temperature rises back to 35°C
- If temperature rises above 36°C, increase flowrate 5 liters per minute every 2 minutes until temp falls below 36°C

Remove the nasal cannula and the air delivery tube and dispose of them properly

Once out of the MRI suite, record the patient temperature (°C) using the 3M SpotOn® zero-heat-flux forehead sensor, the Braun ThermoScan 7 tympanic sensor

Monitor the participant's core body temperature until it returns to baseline. Blankets can be applied to help with warming.

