12 DATA ANALYSIS

12.1 Primary Analysis

The time and flow rate that is required to reduce and maintain each participant's core temperature to 35.5°C from measured baseline temperature will be calculated. The total number of participants who reach the target temperature in 2 hours or less will be calculated.

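### The protocol will report the flow 'required' and cooling as a function of flow, but flow is not set independently of the participant's response, so the data describe the flow delivered

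*Protocol*

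**What the plan says.** Two statements in the Protocol treat flow as an input whose effect will be learned.

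- 2.2 Study Objective: "The study is designed to gather preliminary data regarding air flow rates and time required to reduce core body temperature to 35.5°C". It adds that the data will support automated cooling models and the control algorithm "by examining participant cooling response as a function of air flow rate and time the air is supplied to the participants".
- 12.1 Primary Analysis promises a calculation of "The time and flow rate that is required to reduce and maintain each participant's core temperature to 35.5°C".

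The procedures determine how flow actually varies.

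- 7.6.1, start: "Turn on gas and set flow meter to 35 liters per minute". This applies to every participant.
- 7.6.3, induction: "The flow can be increased to 40 liters per minute after 10 minutes". No criterion says for whom or when. Section 3.1 gives 40 L/min as the most the device can deliver.
- 7.6.3, maintenance: "Adjust flow rate by 5 liters per minute from baseline every 2 minutes". Two conditions follow. Flow goes down in 5 L/min steps while temperature is below 35°C and up in 5 L/min steps while it is above 36°C.
- 7.6.3, records: core temperature every 2 minutes, and every adjustment with its time and reason.

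The study is single-group and open label, and 10 participants are to complete it. No section sets flow independently of how the participant is cooling, and none defines what makes a flow the required one.

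**The concern.** A required flow is a statement about what would have happened at another flow: less would have failed. Each participant follows one flow path, so the record shows a flow under which the target was or was not reached, with no comparison at a lower flow in induction.

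The variation in flow also comes partly from the outcome. In induction, staff who see slow cooling have a natural reason to use the optional increase, so high flow may mark slow coolers. In maintenance, outside the 35-36°C band, temperature moves flow by rule. In both phases higher flow can appear beside slower cooling or higher temperature even if flow cools exactly as intended.

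At stake is the stated use of the data. A control algorithm tuned to a flow-outcome association of this kind would inherit its bias, and a primary result labelled as required flow would claim more than was observed.

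**Working it through.** The Protocol gives no cooling rate, variance or flow-response figure, so there is nothing to reproduce. The check asks how far a simple comparison can be off. Every rate, coefficient of variation (CV), noise level and time constant below is an assumption.

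**Inputs from the Protocol.** Flow 35 then optionally 40 L/min (7.6.1, 7.6.3), ratio 40/35 = 1.143. Baseline 36.8-37.5°C (6.1), target 35.5°C, 2 hours: a fall of 1.3-2.0°C, or 0.65-1.0°C/h. N = 10.

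**Induction, three uses of the discretion.**
- Nobody is stepped up: there is no flow contrast.
- Everyone is stepped up at 10 minutes: flow cannot be separated from elapsed time.
- Some are stepped up: the contrast depends on who they are.

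**Third case.** Assume rate = a × flow, mean 0.8°C/h at 35 L/min, normal variation between people. True gain from the step = 0.8 × (40/35 - 1) = 0.114°C/h. Suppose the slower five of ten are stepped up, ranked without error. The mean distance of each half from the centre is the average of the upper five expected normal order statistics: (1.539 + 1.001 + 0.656 + 0.376 + 0.123)/5 = 0.739 SD. Then

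contrast = 0.8 × [(40/35)(1 - 0.739 CV) - (1 + 0.739 CV)] = 0.114 - 1.267 CV.

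This crosses zero at CV = 0.114/1.267 = 0.09. Simulation (20,000 studies per row) agrees. The noisy-ranking column adds a reading error of SD 0.6°C/h to the early rate.

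| CV | Contrast, perfect ranking (°C/h) | Wrong sign | Contrast, noisy ranking (°C/h) | Wrong sign |
|---|---|---|---|---|
| 5% | +0.051 | 0.2% | +0.110 | <0.1% |
| 10% | -0.012 | 63% | +0.097 | 4% |
| 20% | -0.139 | 99% | +0.049 | 32% |
| 30% | -0.265 | >99.9% | -0.028 | 57% |

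**Same question in minutes to 35.5°C.** Assume 0.9°C/h (SD 0.2) at 35 L/min, fall uniform on 1.3-2.0°C, step at 10 minutes. With perfect ranking the stepped-up half takes about 25 minutes longer. Using only times within the 2-hour limit, the difference falls to about 9 minutes. With a reading error of SD 0.3°C/h and no 2-hour limit it is also about 9 minutes; with SD 0.6°C/h it is close to zero.

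**Maintenance.** Assume a first-order temperature model: time constant 1.5 h, steady fall 2.2°C at 35 L/min, noise 0.02 or 0.05°C per 2-minute step, CV 10-30%, the two conditional rules of 7.6.3, cap 40 L/min, 60 minutes. About 400 studies per setting:

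| Analysis | Wrong sign, range over settings |
|---|---|
| Temperature on flow, pooled readings | 73-99% |
| Participant mean temperature on mean flow | 52-97% |
| Next 2-minute temperature change on current flow | 1-4% |

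The last row is favourable partly by construction: the model form was right, temperature was read without error, and flow on entering maintenance was random.

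**The case against.** **No flow-group comparison is planned.** The endpoints in 5.1 contain no flow-response estimate, 12.1 works participant by participant, and 2.2 calls the data preliminary. A model's form may properly be left to an SAP. This largely stands, and it limits the point to the claim made for flow. It does not rescue the word *required*, which the Protocol itself puts in the primary analysis. How flow is set is a design matter that an SAP can only partly repair.

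**A reader might infer that the response to flow cannot be learned at all.** The documents do not support that. Time-stamped flows, reasons and 2-minute temperatures form a within-person history, and the time-ordered analysis kept the right sign in nearly all simulated studies. Stepping flow in maintenance until temperature returns to the band also says something about each person's need. And under the two stated conditions temperature moves flow only outside 35-36°C, although the unconditional adjustment line is unclear.

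**A reader might infer that the sign will be wrong.** That needs staff to rank people well at about 10 minutes. At 0.9°C/h (SD 0.2) the fall by then averages 0.15°C with a between-person SD of only 0.033°C. The Protocol does not say how the discretion will be used.

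**A reader might infer that flow should be allocated in advance.** That would be a rule for delivering the device's output, which is not proposed here. It would also not make ten participants enough: with the step given to a random half, the sign is still wrong by chance in about 2% (CV 10%) to 30% (CV 40%) of simulated studies. It would affect the first primary endpoint too: in the minutes model, 37% of those held at 35 L/min miss the target, against 22% of those stepped up.

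**Conclusion.** The point holds as a mismatch between claim and design. Under 7.6.3 flow is discretionary in induction and temperature-driven outside the band in maintenance, so the study can describe the flow delivered but does not by itself show the flow required. Pooled or between-participant comparisons of flow with outcome are confounded. They may have the wrong sign, or nearly the right value, depending on who is stepped up, how variable people are and which analysis is used. The simulated frequencies run from under 1% to over 99% on assumed inputs, and none should be quoted alone. That flow is not set independently of response rests on the text and needs no assumption.

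The reach is limited. The count reaching 35.5°C within 2 hours is not touched, and a careful time-ordered model remains possible as exploratory work.

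**What to change.** - **12.1:** replace *required* with *delivered*, and report each participant's flow and time history descriptively for reduction and maintenance.
- **2.2:** state that flow-response data are exploratory and response-driven. Add that any flow-response model should use the time-ordered history, that is, temperature change after each recorded flow setting, with safety- and temperature-driven changes flagged from the recorded reasons. It should not use pooled or between-participant comparisons of flow with outcome. Align the Synopsis objective.
- **7.6.3 with 2.2:** the sponsor should reconcile the discretionary flow line with the flow-response aim, and clarify the unconditional adjustment line. No flow rule is proposed here.
- **Related contradictions that decide which flow records exist:** 2.3.2 adjusts flow and temperature for severe shivering, while 7.6.3 discontinues cooling. Section 4.1 takes the participant off the device at the endpoint, while 7.6.3 continues into maintenance. These passages must be reconciled.

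Cost: rewording in two sections, the Synopsis and the procedure text. No extra participants, and no new data, since adjustments, times and reasons are already recorded. The downside is a more modest claim about flow.

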2.3 Risk and Benefit Assessment

2.3.1 Potential Risks

The only known study-related risk is the use of a nasal cannula to deliver cold air to the participant. The potential risks associated with this delivery are:

Nosebleed

Shivering

Irritation of the nasal passages

Skin irritation at the site of the cannula

Nasal congestion

Over cooling

Participants will be de-identified using a study specific number at the time of enrollment. All Case Report Forms (CRFs) will be labeled with the de-identified participant identification (ID) number. No identifiable participant identification information will be provided to NeuroIntact.

Information collected for this study is confidential. However, officials of the Food and Drug Administration (FDA) or other regulatory agencies may research records during the ordinary course of carrying out their functions. A Sponsor representative may also inspect the research records to make certain the study data is accurate. The Investigator, regulatory agencies, and the Sponsor will protect the confidentiality of the records.

2.3.2 *Risk Mitigation*

The protocol has been designed to minimize the risks to study participants enrolled in the study. In general:

- Prior to study enrollment the Investigator must ensure the participant meets the inclusion/exclusion criteria
- Each participant will be fully informed about the conditions of study participation, and the risks and potential benefits of the study procedure and asked to provide an executed Informed Consent prior to being enrolled in the study
- Institutional Review Board (IRB) review and approval of the study protocol, Informed Consent Form, and any other participant-facing documents will be obtained prior to study initiation.
- The participant's core temperature will be continuously monitored with direction to adjust the VCool if the core temperature is $<35^{\circ}\text{C}$ for a sustained period of 5 minutes, to mitigate overcooling of the participant
- If the participant develops a nosebleed, the VCool will be stopped
- Participants will be assessed for shivering and if severe according to the Bedside Shivering Assessment Scale, the VCool flow and temperature will be adjusted

2.3.3 *Potential Benefits*

The information obtained in this study will not benefit the study participants directly but may aid future patients requiring cooling of body temperature.

2.4 *Study Rationale*

The two leading categories of TTM devices include surface cooling systems and intravascular cooling systems, both of which have disadvantages. Surface systems limit patient access, are difficult to transport, and can cause skin irritation and shivering. Intravascular systems require an invasive procedure and can lead to infection. Both approaches are also intolerable to awake patients. The VCool Intranasal Cooling System is anticipated to overcome these issues as well as cool patients rapidly and be easy to use.

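### Severe shivering (BSAS grade 3) has two incompatible instructions: section 2.3.2 adjusts the device settings, section 7.6.3 discontinues cooling

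*Protocol*

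**What the plan says.** Section 2.3.2 lists the measures meant to limit risk to participants. On shivering it says: "Participants will be assessed for shivering and if severe according to the Bedside Shivering Assessment Scale, the VCool flow and temperature will be adjusted". The bullet just before it covers nosebleeds: "If the participant develops a nosebleed, the VCool will be stopped".

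Section 7.6.3 gives the operating steps. BSAS is scored every 10 minutes, and grade 3 is defined as "Severe: Generalized shivering or sustained upper and/or lower extremity shivering". Mild shivering is met with a regular blanket. For "Moderate or severe" shivering the instruction is "discontinue cooling treatment". The same section tells staff how to document a change of settings: "Record any VCool System adjustments to flow rate or temperature and record the new flow rate and temperature and time of adjustment".

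Two further statements carry the consequence into the results. Section 12.1 says: "The total number of participants who reach the target temperature in 2 hours or less will be calculated". In section 7.6.3, entry to the one-hour maintenance period depends on the target: if the participant's "core body temperature reaches 35.5°C, proceed to the next steps".

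**The concern.** Both sections address the same device, scale and grade, yet they prescribe different actions. A device whose flow and temperature have been reset is still in use; a discontinued treatment is not.

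Three things are at stake.

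- **Participant protection.** Shivering is a listed risk (section 2.3.1) and an anticipated adverse event (section 11). Participants are healthy volunteers with no direct benefit (section 2.3.3). The section that explains how risk is limited describes a different response from the one in the procedure.
- **Compliance.** Section 13.2 counts any failure to follow the protocol's requirements as a deviation. Read literally, either action at grade 3 departs from one section.
- **Results.** Whether cooling goes on or ends can decide whether a participant reaches 35.5°C within 2 hours, and so whether that participant enters the maintenance hour.

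**Working it through.** The protocol states no figure on this point, so the check is mainly a comparison of text.

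**Step 1: the instructions by grade.**

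| BSAS grade | Section 2.3.2 | Section 7.6.3 | Compatible? |
|---|---|---|---|
| 0, none | no action stated | no action stated | yes |
| 1, mild | no action stated | regular blanket | yes; 2.3.2 is silent |
| 2, moderate | no action stated | discontinue cooling | differs by implication only |
| 3, severe | adjust flow and temperature | discontinue cooling | no |

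One of the four grades has two incompatible stated actions. One more differs only if silence in section 2.3.2 is read as meaning no action.

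**Step 2: could adjusting include stopping?** Section 2.3.2 has a separate word for stopping and uses it for nosebleeds ("If the participant develops a nosebleed, the VCool will be stopped"). Section 7.6.3 treats an adjustment as a move to new values to be written down ("Record any VCool System adjustments to flow rate or temperature and record the new flow rate and temperature and time of adjustment"). The shivering bullet names flow and temperature, which are settings of a running device. On this evidence the protocol keeps the two actions apart.

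**Step 3: is there a sequence or an order of precedence?** Neither section describes adjusting first and stopping later. Section 7.6.3 goes directly to discontinuation, and no statement elsewhere ranks one section above the other.

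**Step 4: possible effect on the 2-hour result.** Sections 4.3 and 12.3 give 10 participants. For each participant who scores 3 before reaching the target:

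- same result under either action: change in the count = 0, and 0/10 = 0 percentage points;
- different result: change in the count = 1, and 1/10 = 10 percentage points.

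Section 12.1 plans the count; the percentage is that count over 10. The range assumes the participant stays among the 10.

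**Step 5: what cannot be computed.** The protocol gives no expected shivering rate and no size or direction for the adjustment. It also does not say whether discontinued cooling may resume. No likely overall shift can therefore be derived. The incidence of any shivering (section 12.2) is not changed by the choice of action at the first score, because that score comes before either action.

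**The case against.** The best counter-argument is that section 2.3.2 uses its verbs loosely. For a core temperature below 35°C for 5 minutes it also speaks of adjusting the VCool, yet section 7.6.3 handles that trigger by removing the cannula and resuming later. So the word covers an interruption of cooling at least once. The nosebleed contrast is not perfect either: section 7.6.3 ends the study for a nosebleed but only the cooling for shivering, so the two verbs in 2.3.2 might separate stopping the study from stopping treatment.

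This stands in part. It weakens the argument from word choice but does not remove the conflict, because the shivering bullet specifies flow and temperature where the low-temperature bullet speaks only of the device.

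It can also be said that section 2.3.2 is a summary, introduced as general, and that staff would work from 7.6.3. That lowers the chance of an error at the bedside. But a summary may leave out detail; it may not state a different action. The fair criticism that silence on grade 2 is not a contradiction is accepted, and grade 2 is marked as implication only. It is also fair that the 0 to 10 point range is a bound for one participant and does not forecast an effect.

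**Conclusion.** The inconsistency is real and must be fixed. At BSAS grade 3 the protocol gives two actions that cannot both be carried out, and nothing in it resolves them. The weight of the point rests on this being a safety rule for healthy volunteers, not on a demonstrated effect on the results.

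The possible effect on the 2-hour result is 0 or 1 participant out of 10 for each grade 3 score before target, and the total is unknown. The conclusion assumes that adjusting flow and temperature means continuing on changed settings, which is the plain reading and matches how section 7.6.3 records adjustments. No view is taken on which action is clinically right.

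**What to change.** Reconcile sections 2.3.2 and 7.6.3 so that each BSAS grade leads to one stated action, worded the same way wherever it appears. The sponsor decides which action applies at which grade. If a sequence of actions is intended, the text should say so in both places.

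As a minor addition, report how many participants had cooling adjusted and how many had it stopped because of shivering, so that the 2-hour count can be read in that light. Section 7.6.3 already has the time and reason of each adjustment recorded, and section 8 the primary reason when a participant discontinues the study. This reporting could equally be specified in the SAP, and the main correction does not depend on it.

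The cost is a wording amendment to one or both sections, with site staff informed of the reconciled rule. The design and the sample size do not change.
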